7. STUDY PROCEDURES

7.1 Schedule of Evaluations

Assessments	Historical practice: Baseline overuse (Month - 17 to Month 0)	Baseline, Enrollment, Randomization (Month 0, Day 1)	Intervention Start (Month 1)	Monitored and Measured Monthly	Intervention End (Month 18)	Follow-up Period (Month 19 to Month 30)
Clinician-level Assessments						
Informed Consent		X				
Demographics		X				
Inclusion/Exclusion	X					
Provider Attitudes Survey		X			X	
Patient-level Assessments						
ICD-10 codes	X	X	X	X	X	X
Ordering	X	X	X	X	X	X
Adverse Events	X		X	X	X	

7.2 Description of Evaluations

7.2.1 Consent. We will send providers at participating sites an introductory email that includes a description of the broad goals of the study, a general description of the intervention, and a link to the electronic consent form and baseline survey. The consent document will indicate that participation is voluntary and that decisions to participate (or not) will have no bearing on any provider's status at his or her clinic. Providers who provide consent to participate will be asked to complete an online survey and brief educational session prior to the intervention phase, permit de-identified patient records pertaining to eligible patients who saw them to be included in the study database, and complete a 15-minute post-intervention survey. We will also describe compensation that providers will receive for participation.

7.2.2 Enrollment. The enrollment date will be documented on the online consent form at the time of consent. The interventions will be activated after all clinicians have been enrolled or declined to participate.

7.2.3. Baseline assessments. We will collect information about the rates of each of the 3 co-primary outcomes monthly for the 12 months leading up to the activation of the intervention. This period will document historical practice. We will also administer a survey to assess provider characteristics and provider attitudes toward practice guidelines, clinical decision support, and practice environment.

8. SAFETY ASSESSMENTS

We did not study any safety endpoints related to the PSA primary outcome. The safety endpoints related to the UA/UC and DM primary outcomes were deemed serious adverse events, and included:

- EHR-identified ED or hospital care possibly due to UTI or sepsis among women 65 and over following an office visit
- EHR-Identified ED or hospital care possibly due to hyperglycemia among previously tightly controlled
- Poor diabetes control ($\text{HbA1c} > 9\%$) among individuals who were previously tightly controlled ($\text{HbA1c} < 7\%$)

The Principal Investigator will report any unanticipated events to the IRB as well as the Data Safety and Monitoring Board (DSMB) assembled for this study. When notified of an unanticipated event, the DSMB will convene and make a decision as to whether the study should continue. The IRB will also be notified of the DSMB's decision.

8.1 Safety Monitoring and Reporting Procedures

The Principal Investigator will report any unanticipated events to the IRB as well as the Data Safety and Monitoring Board (DSMB) assembled for this study (listed in Section 14 below). When notified of an unanticipated event, the DSMB will convene and make a decision as to whether the study should continue. The IRB will also be notified of the DSMB's decision.

9. INTERVENTION DISCONTINUATION

Following each DSMB meeting, the board will make recommendations to the local IRBs as to whether the study should continue or if changes to the protocol are necessary for continuation.

10. STATISTICAL CONSIDERATIONS

10.1 General Design Overview

Hypotheses

Our primary hypothesis is that practices randomized to receive behavioral economic interventions will have decreases over time in the over-screening, over-treatment, and over-testing of older patients who

may no longer warrant such care. This hypothesis will be evaluated in an intention-to-treat difference-in-differences framework using a mixed-effects logistic regression model. Fixed effects will include the effects of interventions over time (i.e., interactions between randomization assignment and time), using a historical period 12 months prior to the intervention period. Providers and randomization unit (clinic) will be modeled as random effects.

Design

We will conduct a cluster randomized trial using data abstracted from the EHR at one academic health system. We chose a cluster-randomized design at the clinic level to minimize spillover effects – contamination that might occur if individual providers in close proximity are randomized to different interventions. The study design for BEAGLE included the implementation of a modified constrained randomization scheme, to ensure that clinics in each study arm were similar prior to activation of the intervention.

Outcome measures

This study has 3 co-primary outcomes, referred to as PSA, UA/UC, and DM (defined in Section 6 above, and further detailed in Section 10.4 below). They capture the over-testing, over-screening, and over-treatment of older patients, whose medical needs may have evolved to require less care.

10.2 Sample Size and Randomization

Power Calculations

Study power for BEAGLE was designed around estimating minimum detectable absolute rate reductions for the three co-primary outcome measures at the individual level. Power calculations were done for a 2-level mixed effects logistic regression model that included a random intercept for clinic using PASS software. Historic data, from a period spanning X, 2017 – Y, 2018 were used to estimate an inter-clinic correlation coefficient of 0.017. In all calculations, we assumed a two-sided type I error of 5% (Bonferroni-corrected to $0.05/3 = 0.017$), 80% power, 30 clinics in each arm, and that patients would be divided equally between clinics in 2 groups. Initial calculations assumed baseline event rates and sample sizes described in Table 1. These analyses should have been conservative, as our assumed sample size was derived from an historic 12-month period, while the study follow-up period was 18 months. We did not assume any clinic drop-out, as all data will be available via the EHR. With these assumptions, we anticipated having adequate power to detect an absolute difference of roughly 4% for each of the measures. For the PSA and UA/UC outcomes, this corresponded to a relative risk between 0.80 and 0.87; for the DM outcome, it corresponded to a relative risk between 0.73 and 0.81.

Table 1. Summary of power calculations for the BEAGLE study.

	PSA N=9,500			DM N = 6,600			UA/UC N = 15,000		
	20%	25%	30%	15%	20%	25%	20%	25%	30%
Baseline event rate	20%	25%	30%	15%	20%	25%	20%	25%	30%
Minimum detectable absolute rate reduction	4.1%	4.5%	4.8%	3.9%	4.4%	4.8%	3.8%	4.2%	4.4%
Corresponding relative risk	0.80	0.82	0.84	0.74	0.78	0.81	0.81	0.83	0.85

Treatment Assignment Procedures – Constrained Randomization

Clinics were randomized to receive either the active intervention or control. Clinicians were attributed to precisely one clinic based on the clinic where they spent the plurality of their time in March 2019 – February 2020. All 60 eligible primary care clinics seeing adult patients were randomized. The study design for BEAGLE implemented a modified constrained randomization scheme. Eight clinic-level variables were selected based on their possible influence on the three co-primary outcomes, and were incorporated into the randomization schemes in a principled manner to reduce potential bias and promote comparable arms at the analytic unit (clinician/patient encounter). These clinic-specific variables, created using data abstracted from the EHR, were:

1. Health system region – We categorized each practice into one of four geographic areas in the Chicago area (categorical).
2. Number of clinicians attributed to each practice (continuous).
3. Number of men eligible for PSA overtesting (age 76 years or older, no history of prostate cancer, not on androgenic agents or anabolic steroids) seen in clinic between March 1, 2019 and February 29, 2020 by a participating clinician (continuous).
4. Annual PSA overtesting rate (percentage).
5. Number of women eligible for unnecessary UA/UC testing measure between March 1, 2019 and February 29, 2020 (continuous).
6. Annual UA/UC overtesting rate (percentage).
7. Number of patients eligible for DM overtreatment measure between March 1, 2019 and February 29, 2020 (continuous).
8. Annual DM overtreatment rate (percentage).

Six practices only contributed nine months of data (June 1, 2019 – February 29, 2020) because they were acquired by Northwestern Medicine between March 1, 2019 and June 1, 2019.

We used the methodology presented in [cite] to implement the constrained randomization algorithm. First, the study biostatistician ([name]) generated possible 1:1 randomization schemes. Since there were infinitely many ways to randomize the 60 practices into 2 groups, the study biostatistician decided to create 100,000 possible sequences. Second, the balance of the eight prespecified variables (which were “constrained” upon) was then evaluated in the 100,000 possibilities. Schemes were deemed candidate schemes if they had “adequate balance” – that is, the measure of imbalance for each variable (separately) could not surpass a pre-specified threshold. For categorical variables, we allowed no more than a difference of two practices across each arm. For continuous variables, we compared sample means across study arm, and adapted the ideas of the minimal sufficient balance approach. We called a variable ‘adequately balanced’ if a T-statistic from an independent two sample t-test with equal variance was between -0.385 and 0.385, corresponding to a p-value for the individual variable of 0.30. Last, the final sequence was selected from the candidate schemes (which were adequately balanced) at random with equal probability.

As was disclosed in the study protocol paper, we achieved adequate balance for seven of the eight pre-specified variables used in the constrained randomization algorithm. Due to a coding error, we applied balancing criteria for the PSA measure on the number of eligible patients (denominator) and the number of PSA orders (numerator) rather than the annual PSA overtesting rate (#4 above). This is an absolute measure instead of a relative measure that accounts for the size of the eligible patient population at each clinic. For a complete discussion of the implications of this error, please reference the protocol paper.

The study biostatistician ([name]) generated the final randomization in R version 3.6.4 (R Core Team, 2020). [25] Randomization occurred in June 2020. The allocation of the sequence was concealed until

after the intervention period began in September 2020 (due to interruption of regular care during the COVID-19 pandemic).

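### The stated ICC of 0.017 and Table 1 do not agree under any calculation the text describes: on the proportion scale it gives 4.5–5.7 points, not 3.8–4.8, and the table needs an ICC of about 0.010

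*Combined protocol and SAP*

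**What the plan says.** All of this is in Section 10.2, Power Calculations, unless noted.

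- **Model.** Power was computed in PASS for a "2-level mixed effects logistic regression model that included a random intercept for clinic". No baseline adjustment is mentioned as an input.
- **ICC.** Historic data "were used to estimate an inter-clinic correlation coefficient of 0.017". One value serves all three outcomes. Its scale is not given, and the months of its source period are still the letters X and Y.
- **Other inputs.** The calculation assumed "a two-sided type I error of 5% (Bonferroni-corrected to $0.05/3 = 0.017$), 80% power, 30 clinics in each arm", equal clinic sizes and no clinic drop-out.
- **Table 1.** N is 9,500 (PSA), 6,600 (DM) and 15,000 (UA/UC). Detectable reductions are PSA 4.1/4.5/4.8 and UA/UC 3.8/4.2/4.4 points at baselines of 20/25/30%, and DM 3.9/4.4/4.8 points at 15/20/25%.
- **Summary.** "we anticipated having adequate power to detect an absolute difference of roughly 4% for each of the measures".
- **Relative risks.** The text then restates this difference on the ratio scale: "For the PSA and UA/UC outcomes, this corresponded to a relative risk between 0.80 and 0.87"; its DM range is 0.73 to 0.81.
- **Margin.** "These analyses should have been conservative, as our assumed sample size was derived from an historic 12-month period", whereas follow-up lasts 18 months.
- **Randomisation** (same section, Treatment Assignment Procedures). "All 60 eligible primary care clinics seeing adult patients were randomized".

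**The concern.** The inputs are complete enough for a reader to recompute Table 1. With 0.017 entered as an ordinary proportion-scale ICC, every cell comes out larger than printed. The paragraph is the only sample-size justification for three co-primary outcomes, and readers will use it to judge a null result.

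As written, a reader cannot choose between three situations:

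- the table is right and the ICC sentence is wrong;
- both are right and a conversion step is missing;
- the ICC is right on the proportion scale and the table is too favourable.

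Only in the third does the stated calculation give less than 80% power throughout the table.

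**Working it through.** **Formula.** With m = N/60 patients per clinic, N/2 per arm, design effect DE = 1 + (m − 1) × ICC and p2 = p1 − d, solve

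d = (z₁₋α/₂ + z₀.₈) × √[(p1q1 + p2q2) × DE / (N/2)].

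For α = 0.05/3 the multiplier is 2.394 + 0.842 = 3.236. Clinic sizes are 158.3 (PSA), 110 (DM) and 250 (UA/UC).

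**Step 1: which ICC returns the printed table?** At ICC 0.0101 the design effects are 2.59, 2.10 and 3.51, and all nine cells match to the printed decimal (table below). The range of ICC compatible with the rounding of all nine cells is 0.01004–0.01022. A t test on 58 df moves the implied value to about 0.0094.

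**Step 2: the stated 0.017 on the proportion scale.** The design effects are 3.67, 2.85 and 5.23. Worked cell, PSA at 20%:

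- Try d = 0.0484, so p2 = 0.1516 and p1q1 + p2q2 = 0.1600 + 0.1286 = 0.2886.
- √(0.2886 × 3.675 / 4,750) = 0.01494, and 3.236 × 0.01494 = 0.0484, so the equation is satisfied.
- Power at the printed 4.1: √(0.2937 × 3.675 / 4,750) = 0.01507; 0.041/0.01507 − 2.394 = 0.33; Φ(0.33) ≈ 63%.

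| Outcome, baseline rates | Printed | ICC 0.0101 | ICC 0.017, proportion scale | Power at printed value, ICC 0.017 |
|---|---|---|---|---|
| PSA 20/25/30% | 4.1/4.5/4.8 | 4.09/4.47/4.77 | 4.84/5.29/5.65 | 63/63/63% |
| DM 15/20/25% | 3.9/4.4/4.8 | 3.88/4.41/4.82 | 4.48/5.10/5.58 | 65/65/65% |
| UA/UC 20/25/30% | 3.8/4.2/4.4 | 3.81/4.16/4.43 | 4.60/5.04/5.38 | 60/61/59% |

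No cell matches at 0.017. Rounding of the ICC (0.0165–0.0175) still gives 4.4–5.7 points.

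**Step 3: was the Bonferroni step left out?** At α = 0.05 the implied ICC runs from 0.0145 to 0.0168 by cell, and no single value fits all nine.

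**Step 4: do 18 months of patients close the gap?** If 18 months brought 1.5 times the patients (an assumption), ICC 0.017 on the proportion scale gives PSA 4.63/5.06/5.40, DM 4.23/4.81/5.26 and UA/UC 4.47/4.88/5.21, with power at the printed values of 63–72%. With unlimited patients, DE/(N/2) tends to 0.017/30, and the limit at 20/25/30% is 4.17/4.56/4.86. That is above all six printed PSA and UA/UC values.

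**Step 5: 0.017 on the latent logistic scale.** The clinic variance is 0.017/0.983 × π²/3 = 0.0569. Integrating over the random intercept gives proportion-scale ICCs of 0.0073, 0.0090, 0.0105 and 0.0117 at 15, 20, 25 and 30%.

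- *Converted cell by cell at the baseline rate:* PSA 3.96/4.53/4.99, DM 3.60/4.29/4.87, UA/UC 3.67/4.22/4.67. Four of nine cells are at or below the printed value, and power at the printed values is 74–87%. If the intervention arm is converted at its own lower rate, the range is 3.5–4.9 points. Both are near the table; neither reproduces it.
- *Converted once:* the mean of the nine baseline rates is (75 + 60 + 75)/9 = 23.3%. There the conversion gives 0.01005, and the cells are 4.09/4.47/4.76, 3.88/4.40/4.81 and 3.80/4.15/4.42, so nine of nine match.

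**Step 6: relative risks.** Table 1 spans 0.80–0.85 (PSA and UA/UC) and 0.74–0.81 (DM). The text's 0.87 and 0.73 are 1 − 0.04/0.30 and 1 − 0.04/0.15, from a flat 4 points. Its DM upper value of 0.81 is the table's 1 − 0.048/0.25; a flat 4 points would give 0.84. The DM range therefore mixes two sources.

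**The case against.** The strongest reply is that ICC, model and table may all be correct. A logistic model with a random clinic intercept naturally yields a latent-scale ICC, and one conversion at the average of the table's own baseline rates returns every cell. This stands as a possibility. It could also be coincidence, and the text describes no conversion, so the step would still have to be reported.

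A second reply is that the consequence is small. All 60 clinics were randomised, so their number cannot change, and the planned analysis is a difference-in-differences model (Sections 10.1 and 10.5), not the comparison that was powered. This also stands. The point concerns a reported planning figure, and the power of the planned model cannot be derived from the documents. Nor can that model explain Table 1, because no baseline adjustment is among the table's stated inputs.

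Two stronger readings are tempting, and the documents support neither. A reader might infer that Table 1 is wrong and the trial underpowered. That follows only if 0.017 is on the proportion scale. A reader might also infer that the ICC was mistyped, because the rounded Bonferroni alpha in the next sentence is the same number. Nothing in the documents links the two figures.

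**Conclusion.** The stated ICC and Table 1 need reconciling, because they agree only through a step that the text does not describe. The arithmetic is firm, but the size of the problem depends on the scale:

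- **Proportion scale:** detectable reductions are 4.5–5.7 points, 0.6–1.0 above those printed (relative risk about 0.70–0.82).
- **Latent scale, converted cell by cell:** 3.6–5.0 points, with no general shortfall.
- **Latent scale, converted once at about 23.3%:** the table stands.

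Which of these applies cannot be settled from the documents. The relative-risk mismatch holds on every reading but is small. The results assume a normal approximation with unpooled variance, equal clinics and a two-arm comparison without baseline adjustment. With a t test on 58 df, proportion-scale 0.017 gives 4.6–5.8 points, so the conclusion does not change.

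**What to change.** Check the PASS output and the historic data. State the ICC estimate, its source period, its scale and the value entered in PASS. Then take one branch:

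1. **If 0.017 is on the proportion scale:** recompute Table 1 and replace the 4-point summary with about 4.5–5.7 points. The 12- versus 18-month remark may stay as true in direction, but it should not be used to support the printed values.
2. **If about 0.010 was estimated and used:** correct the ICC sentence and keep Table 1.
3. **If 0.017 is a latent-scale estimate converted once:** state the conversion and its baseline rate, and keep Table 1.

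In every branch, take the text's relative-risk ranges from the final Table 1. As now printed, these are 0.80–0.85 for PSA and UA/UC and 0.74–0.81 for DM.

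The cost is text and table only, with no extra patients, clinics or analyses. Under branch 1 the stated detectable differences become larger.

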We will recruit clinicians (physicians, advance practice nurses, and physician assistants) from 60 primary care clinics (internal medicine, family medicine and geriatrics) affiliated with Northwestern Medicine. Approximately 350 eligible clinicians will be recruited for this study.

We will randomize practices to intervention or control (1:1 allocation) using a constrained randomization algorithm, to achieve balance between study arms on baseline clinic characteristics.

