10.5 Statistical Analyses

We will use the following descriptive statistics to characterize the sample: Means and medians for continuous measures, frequencies for count data, standard deviations and interquartile ranges for variance.

To test our 3 co-primary hypotheses, we will employ a mixed-effects hierarchical logistic regression model to estimate the adjusted marginal effect over time of each intervention on the 3 co-primary outcomes. Fixed effects will include intervention assignment, time period (historical baseline versus intervention period), time period interacted with intervention assignment, time (continuous, linear), and a 3-way interaction term between time period, intervention, and time (continuous). The coefficient on the 3-way interaction term will represent whether the log-odds of the monthly rate of change in each co-primary outcome differs between intervention and control patients during the intervention period. Providers will be included as random effects. To isolate the effect of the intervention on the co-primary outcomes, we will also include fixed effects for the variables included in the constrained randomization procedure.

The secondary and safety outcomes will be examined in a similar fashion. If they are sufficiently rare (for example, no events in a given month), model convergence may become an issue. First, we plan to expand the time frame from months to quarters and fit the same model. If that fails, we will abandon the time-varying aspect of the analysis and do one pull for the historical baseline period and one pull for the intervention period. The mixed effects logistic regression model would then be run without including continuous time. If that still fails to converge, we will exclude the random effects for providers and use a fixed effects logistic regression model.

Last, the three co-primary outcomes of interest will be examined in the following pre-specified subgroups:

- Sex (DM measures only)
- Race and ethnicity
- Age groups (for UA/UC: 65-74, 75-84, 85+) (for PSA: 76-79, 80-84, 85+) (for DM: 75-79, 80-84, 85+). We will also examine for effects on patients younger than the target populations (for UA/UC: 50-64, PSA: 70-75, DM 65-74).

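### Section 10.5 names no testing procedure for the three co-primary outcomes; if the Bonferroni level assumed for planning in 10.2 is carried into the analysis, Holm would give the same error control with more power

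*Combined protocol and SAP*

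**What the plan says.** Section 10.1 sets the family of tests: "This study has 3 co-primary outcomes, referred to as PSA, UA/UC, and DM". The Précis hypothesises lower rates in all three domains.

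The power calculation in section 10.2 is the only place where an error rate or a multiplicity adjustment appears. It reads "we assumed a two-sided type I error of 5% (Bonferroni-corrected to" 0.05/3 = 0.017), and continues with "80% power, 30 clinics in each arm, and that patients would be divided equally between clinics in 2 groups". The verb and the setting make this a planning assumption.

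Section 10.5 turns to the tests: "To test our 3 co-primary hypotheses, we will employ a mixed-effects hierarchical logistic regression model". It lists the fixed and random effects and identifies the coefficient of interest, a three-way interaction between time period, intervention and continuous time. It states no significance level, no multiplicity procedure and no rule for what counts as success (any one outcome, each on its own, or all three). No stepwise method is mentioned anywhere.

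**The concern.** An analyst looking for the threshold will find only 0.05/3 and will probably compare each of the three p-values with 0.017, whatever the other two show.

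That is valid, but it wastes power when several effects are real, which is what the trial hypothesises. Take p-values of 0.001, 0.010 and 0.030. Bonferroni declares the first two and calls the third negative. Holm compares the ordered values with 0.05/3, 0.05/2 and 0.05 and declares all three, with the family-wise error still at most 5%.

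What is at stake is the conclusion for a second or third outcome whose p-value falls between 0.017 and 0.05. There is also the plainer gap that the analysis section does not say which rule applies.

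**Working it through.** **1. The plan's level.** 0.05/3 = 0.01667, printed as 0.017; it reproduces. For three independent tests with no real effects, the family-wise error is 1 − (1 − 0.01667)³ = 0.049. Holm's is identical there, because its first step is the same comparison.

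**2. Inputs for the comparison.** Two-sided 5% and three tests are from 10.1 and 10.2. The 80% power at 0.05/3 for each real effect is borrowed from 10.2. The correlation between test statistics is assumed (0, 0.3, 0.5), since the documents give none.

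**3. Power of one test at each Holm threshold.** The mean of the z-statistic is z(1 − 0.05/6) + z(0.80) = 2.394 + 0.842 = 3.236.

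- At 0.05/3: 0.800
- At 0.05/2: Φ(3.236 − 2.241) = 0.840
- At 0.05: Φ(3.236 − 1.960) = 0.899

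So a real effect gives p ≤ 0.0167 with probability A = 0.800, p between 0.0167 and 0.025 with B = 0.040, and p between 0.025 and 0.05 with C = 0.059.

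**4. Three real effects, independent tests.**

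- Per outcome, Bonferroni: A = 0.800.
- Per outcome, Holm: A + B × P(at least one of the other two in A) + C × P(both others ≤ 0.025, at least one of them ≤ 0.0167) = 0.800 + 0.040 × 0.960 + 0.059 × (0.840² − 0.040²) = 0.800 + 0.038 + 0.042 = 0.880.
- All three, Bonferroni: A³ = 0.512.
- All three, Holm: A³ + 3A²B + 3A²C + 3AB² + 6ABC = 0.512 + 0.077 + 0.113 + 0.004 + 0.011 = 0.717.

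**5. Fewer real effects, independent tests.** The same formula is used with null probabilities 0.0167 and 0.025 for the outcomes without an effect.

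- Two real: 0.800 + 0.040 × 0.803 + 0.059 × 0.021 = 0.833 per outcome.
- One real: 0.800 + 0.040 × 0.033 + almost nothing = 0.801.

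**6. Correlated tests** (simulation, 1,000,000 draws per setting):

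| Setting | Correlation | Bonferroni | Holm |
|---|---|---|---|
| 3 real, per outcome | 0 / 0.3 / 0.5 | 80% | 88.0 / 87.1 / 86.4% |
| 3 real, all three | 0 / 0.3 / 0.5 | 51.2 / 57.0 / 61.1% | 71.7 / 74.4 / 76.6% |
| 2 real, per outcome | 0 / 0.3 / 0.5 | 80% | 83.3 / 83.0 / 82.7% |
| 1 real | 0 to 0.5 | 80% | about 80.1% |
| At least one rejection | any | same | same |

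Holm rejected everything that Bonferroni rejected in every draw. With one or two real effects, the family-wise error was 0.039-0.046 for Holm and 0.017-0.033 for Bonferroni, all below 0.05.

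**7. Is 80% a sound starting point here?** Not firmly, for two reasons.

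- Table 1 powers a two-arm difference in rates, while 10.5 tests a three-way interaction, for which no power is given.
- Table 1 does not reproduce from its stated inputs by a standard two-proportion calculation with a design effect, using the ICC in 10.2 ("were used to estimate an inter-clinic correlation coefficient of 0.017"). For UA/UC at a 20% rate there are 15,000/60 = 250 patients per clinic. The design effect is 1 + 249 × 0.017 = 5.233, and the effective n per arm is 7,500/5.233 = 1,433. Power for the printed 3.8-point reduction at 0.05/3 is Φ[(0.038 − 2.394 × 0.01438)/0.01437] = about 0.60. Across the nine cells it is 59-65%.

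The table is a separate matter to reconcile. It matters here only because it weakens the 80%. Starting instead from 62%, in the middle of that range, the formulas in steps 3 and 4 give Holm 71% per outcome and 44% for all three, against 62% and 24% (independent tests, three real effects).

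**The case against.** **The plan does not commit to Bonferroni.** A reader might infer that the trial tests each outcome at 0.017 regardless of the others. The documents do not support that: the level is a planning assumption, 10.5 is silent, and planning at 0.05/3 is compatible with Holm because it is Holm's first step. This stands in full. It limits the point to what should be written in 10.5.

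**Nothing is wrong.** Also correct. Bonferroni controls the error, and the documents do not contradict themselves on this. Preferring Holm is a matter of efficiency.

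**The headline gain is a best case.** The rise from 51% to 72% matters only if declaring all three is of interest, and no section requires it. If success did require all three, each could be tested at 0.05 and no adjustment would be needed. Dividing alpha by three suggests that each outcome supports its own claim, but this is an inference. Equal effects are also doubtful on the pilot figures in section 2.2: the test was not done after 13% of PSA alerts, against 62% for UA/UC, and therapy was reduced in 34% of DM patients. These objections limit the size of the gain. They do not touch Holm's property of never rejecting less.

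**It is not wholly free.** An outcome with p = 0.030 can be rejected by Holm while its 98.3% interval includes no effect. This is a real but small reporting cost.

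**Timing.** Sections 10.3 and 11.2 are partly in the past tense, and tenses are mixed throughout, so the documents do not settle whether results had been seen. If they had, moving to a more lenient rule would be post hoc.

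**Conclusion.** The point holds as a nearly free improvement. The only adjustment in the documents is a planning level, and the analysis section states no procedure. If the planning level became the testing rule, it would be dominated by Holm, which has the same strong 5% control under any dependence. That dominance needs only valid p-values and does not depend on the power assumptions.

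The size of the gain does depend on them. With 80% power per test at 0.05/3 and three real effects, the gain is about 6-8 percentage points per outcome and 16-21 points for all three (76.6 − 61.1 = 15.5 at correlation 0.5; 71.7 − 51.2 = 20.5 at 0). With two real effects it is about 3 points per outcome. With one it is about 0.1, and for at least one rejection it is zero.

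A reader might take these figures as power that this trial will lose. The documents do not support that reading, because neither the 80% starting point nor the correlation is established for the interaction test in 10.5.

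**What to change.** In section 10.5, before outcome results by arm are seen, add two sentences. The first should say that each co-primary outcome supports its own claim. The second should say that the three p-values are tested by the Holm step-down procedure at a family-wise two-sided 5%.

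Keep 0.05/3 in section 10.2, described as the conservative planning level (Holm's first step).

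If confidence intervals stay at the Bonferroni level, say in the report that they do not correspond to the step-down test and may include no effect for an outcome that Holm rejects.

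The cost is a few sentences, with no extra data and no loss of family-wise error control. If results by arm have already been seen, the change should not be presented as prespecified.

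### Section 10.2's text gives detectable relative risks up to 0.87 for PSA and UA/UC, but its own Table 1 stops at 0.85, and power at 0.87 falls short of 80%

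*Combined protocol and SAP*

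**What the plan says.** All of this is in the Power Calculations part of section 10.2. The calculation is for a "2-level mixed effects logistic regression model that included a random intercept for clinic using PASS software". Its main assumptions are: "we assumed a two-sided type I error of 5% (Bonferroni-corrected to $0.05/3 = 0.017$), 80% power, 30 clinics in each arm". Clinic sizes are taken as equal: "patients would be divided equally between clinics in 2 groups". Historic data "were used to estimate an inter-clinic correlation coefficient of 0.017".

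The text then summarises the result as a detectable absolute difference of about 4% for every measure. For PSA and UA/UC it adds that "this corresponded to a relative risk between 0.80 and 0.87; for the DM outcome, it corresponded to a relative risk between 0.73 and 0.81".

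In the row "Corresponding relative risk", Table 1 gives PSA 0.80, 0.82, 0.84; UA/UC 0.81, 0.83, 0.85; and DM 0.74, 0.78, 0.81. The section also says of the calculations that "These analyses should have been conservative", because the patient numbers come from 12 months while follow-up lasts 18.

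**The concern.** The text and the table report one calculation but disagree at two ends. No cell of Table 1 shows 0.87 or 0.73. The weakest effect in the table for PSA or UA/UC is 0.85, a 15% relative reduction; the text implies that a 13% reduction is detectable with the planned power.

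This summary sentence is the one likely to be cited when a non-significant co-primary result is interpreted. If it claims more sensitivity than the calculation gave, the trial will seem to have excluded effects it was not powered to find.

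**Working it through.** **Inputs (section 10.2).** Two-sided alpha 0.05/3 = 0.0167 (z = 2.394); 80% power; 60 clinics, 30 per arm, of equal size; printed ICC 0.017; N = 9,500 (PSA), 6,600 (DM), 15,000 (UA/UC); baselines and reductions from Table 1.

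**1. Is Table 1 consistent with itself?** RR = 1 - reduction/baseline.
- PSA: 1 - 4.1/20 = 0.795; 1 - 4.5/25 = 0.82; 1 - 4.8/30 = 0.84.
- UA/UC: 1 - 3.8/20 = 0.81; 1 - 4.2/25 = 0.832; 1 - 4.4/30 = 0.853.
- DM: 1 - 3.9/15 = 0.74; 1 - 4.4/20 = 0.78; 1 - 4.8/25 = 0.808.

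Every printed RR is recovered within rounding. The ranges are 0.80-0.85 (PSA and UA/UC) and 0.74-0.81 (DM).

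**2. Where might 0.87 and 0.73 come from?** A flat 4% gives 1 - 4/30 = 0.867 and 1 - 4/15 = 0.733. At 30%, however, the table's minimum is 4.8 points (PSA) and 4.4 points (UA/UC). The text's upper DM value, 0.81, is the table's; a flat 4% would give 1 - 4/25 = 0.84. So the sentence seems to mix two bases.

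**3. Does Table 1 follow from the stated inputs?** With m = N/60, the effective number per arm is n = (N/2)/[1 + (m - 1) x ICC]. I solved a two-proportion test on n for the reduction that gives 80% power.

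| Outcome (baselines) | Table 1 (points) | ICC 0.010 | ICC 0.017 | RR at ICC 0.017 |
|---|---|---|---|---|
| PSA (20/25/30%) | 4.1/4.5/4.8 | 4.09/4.46/4.76 | 4.84/5.30/5.66 | 0.76/0.79/0.81 |
| DM (15/20/25%) | 3.9/4.4/4.8 | 3.88/4.40/4.81 | 4.49/5.10/5.59 | 0.70/0.75/0.78 |
| UA/UC (20/25/30%) | 3.8/4.2/4.4 | 3.80/4.15/4.42 | 4.61/5.04/5.38 | 0.77/0.80/0.82 |

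The printed ICC of 0.017 reproduces no cell. An ICC of 0.010 reproduces eight of nine to rounding; the ninth is 4.15 against 4.2.

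**4. Power at RR 0.87 from the most favourable baseline, 30%.** Here p2 = 0.87 x 0.30 = 0.261, a difference of 0.039. SE = sqrt[(0.30 x 0.70 + 0.261 x 0.739)/n], and power = Phi(0.039/SE - 2.394).

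| | Design effect | n per arm | SE | 0.039/SE - 2.394 | Power |
|---|---|---|---|---|---|
| PSA, ICC 0.010 | 2.573 | 1,846 | 0.01477 | 0.25 | 60% |
| UA/UC, ICC 0.010 | 3.490 | 2,149 | 0.01369 | 0.46 | 67% |
| PSA, ICC 0.017 | 3.675 | 1,293 | 0.01765 | -0.18 | 43% |
| UA/UC, ICC 0.017 | 5.233 | 1,433 | 0.01677 | -0.07 | 47% |

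Pooled variance gives the same results. At a 25% baseline, power is 48% (PSA) and 55% (UA/UC) at ICC 0.010, and 33% and 37% at 0.017. If 0.017 is read as a latent (logit-scale) ICC, power at the 30% baseline is 55% and 62%.

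**5. Does longer follow-up rescue 0.87?** Granting a full 1.5 x N at the 30% baseline, power is 67% (PSA) and 73% (UA/UC) at ICC 0.010, and 47% and 50% at 0.017. The number of clinics stays at 60, so the gain is limited.

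**6. DM at RR 0.73, 15% baseline.** Power is 84% at ICC 0.010 and 69% at 0.017.

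**The case against.** **It is only a rounding slip, with the exact values printed just below.** That is probably the cause, and it makes this a reporting error rather than a second power calculation. But the step from 0.84 or 0.85 to 0.87 takes power from about 80% to 60% (PSA) and 67% (UA/UC) on the table's own basis, so the wording needs correcting.

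**The 43% and 47% mix two problems.** This stands. At ICC 0.017, power at Table 1's own 30%-baseline cells is already only 63% (PSA) and 59% (UA/UC). Much of the shortfall there is the mismatch between the ICC and the table. The part due to the text is best read from the ICC 0.010 figures.

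**A reader might infer that the design cannot detect a 13% reduction.** The documents do not support that. The planned model (sections 10.1 and 10.5) uses a 12-month baseline period and adjusts for the randomization variables, which include clinic baseline rates. By the formula above, 80% power at 0.87 from a 30% baseline would need a residual ICC of about 0.0045 (PSA) or 0.0068 (UA/UC). No residual ICC is given, and testing a three-way interaction with time could lower power. Power under the planned model is therefore unknown.

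**A reader might link 0.87 to the pilot's 2 of 15 PSA alerts (13%) after which no test was done.** That is an uncontrolled share of alerts, not a reduction in a patient-level 365-day rate. Nothing in the plan makes 13% a target.

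**A reader might want the sentence calling the calculations conservative removed.** Its stated reason points the right way. Unequal clinic sizes would work against it, but the power section gives no measure of their spread. It can stay; it just does not justify 0.87.

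**Conclusion.** Wrong as written. The text's range for PSA and UA/UC exceeds what Table 1 supports: 0.87 against 0.85. Within the stated power framework, power at 0.87 is about 60% (PSA) and 67% (UA/UC) at ICC 0.010 and about 43% and 47% at ICC 0.017, all at the most favourable baseline. No variant tried reaches 80%.

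A reader might count the DM figure as a second overclaim. It is not one relative to the table: 0.73 is a slightly larger effect than 0.74 and so easier to detect. It is a 0.01 inconsistency.

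These figures rest on a design-effect approximation to the PASS routine, equal clinic sizes and no baseline adjustment. The close match to Table 1 at ICC 0.010 suggests the approximation is adequate. That 0.010 was the value actually used is an inference; the documents print 0.017.

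**What to change.** 1. Confirm the ICC used in the calculation.
2. If Table 1 stands, replace the single figure of about 4% with the table's range, 3.8-4.8 points. Restate the relative risks as 0.80-0.85 for PSA and UA/UC and 0.74-0.81 for DM, and correct the printed ICC.
3. If 0.017 is the true ICC, recompute Table 1 and the text together. By the approximation above, the detectable reductions become about 4.5-5.7 points, with relative risks of about 0.76-0.82 (PSA, UA/UC) and 0.70-0.78 (DM).

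Changing the text alone to match the table would leave the ICC conflict in place. The cost is an edit, plus one rerun of the power software if the ICC is 0.017. No endpoint, model, alpha or sample size changes; the stated sensitivity becomes somewhat less favourable.
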